The current proposal will assess the risks and benefits of the use of oral bisphosphonates to prevent fragility fractures amongst patients with stage \geq 3B CKD. Oral bisphosphonates are the first line therapies for the primary and secondary prevention of osteoporotic fractures, as recognized by NICE guidelines (TA 160 and 161), but they are contraindicated in patients with eGFR<30-35. The drugs assessed will be the currently recommended ones: oral alendronate, risedronate, and ibandronate.

Use of oral bisphosphonates will be identified using pre-specified lists of the British National Formulary (BNF) within CPRD, and Anatomic Therapeutic Classification (ATC) codes for OUHD (Appendix 1).

There is no approved alternative bone medication for patients with severe CKD, and therefore oral bisphosphonate users will be compared to those not on anti-osteoporosis therapy (i.e. drug non-users).

EXPOSURE PERIODS

As the data sources include information on drug prescribing (CPRD) or dispensing (OUHD) as opposed to drug consumption, the prescription duration may not reflect the true number of days over which a prescription was used. As a result, assumptions will be made to account for non-adherence (or non-compliance) in order to define periods of continuous exposure.

We will assume that any overlap between two prescriptions of the same bisphosphonate represent early collection of a repeat prescription. Hence, any overlapping days between two prescriptions of the same drug will be added to the end of the period covered by the two prescriptions. In order to define periods of continuous use of study drugs, any two prescriptions of the same drug will be concatenated if the gap between the end of the first of the two prescriptions and the start of the second of the two prescriptions was less than 30 days apart.

DESIGN AND THEORETICAL/CONCEPTUAL FRAMEWORK

CONCEPTUAL FRAMEWORK

An observational cohort study using routinely collected data will be performed to evaluate the potential risks (CKD progression, hypocalcaemia/hypo-phosphatemia, and a number of adverse events) and benefits (bone density improvement, and fracture protection) observed amongst patients with stage ≥3B CKD in actual 'real life' NHS practice.

STUDY DESIGN

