The chosen study design is a propensity score-matched retrospective cohort study. This is one of the best pharmaco-epidemiological designs available for the assessment of intended (benefits) and unintended (risks) effects of drugs in observational data. Propensity score-matching will therefore be used to match each eligible bisphosphonate user to 5 non-users, producing matched comparable (in terms of observed baseline characteristics) cohorts.

TARGET POPULATION

The target population of this study will be patients with an eGFR<45 (based on serum creatinine) aged 40 years or older at the age of biochemistry testing.

EXCLUSION CRITERIA

From the population described above, we will exclude those with any of the following exclusion criteria:

- Less than 1 year of follow-up data available within the data source/s.
- CPRD participants with no possible linkage to HES.
- Use of anti-osteoporosis medication/s in the previous year (except calcium and/or vitamin D supplements).
- Use of any (except calcium and/or vitamin D supplements) other anti-osteoporosis medication/s (other than bisphosphonates).

SETTING/CONTEXT

Setting: The proposed study will obtain data from both primary (CPRD) and secondary (HES) care.

Study period: Currently used oral bisphosphonates (alendronate, risedronate and ibandronate) were approved and launched to the market in 1996 onwards. Our study period will therefore cover from 1996 to the latest data extraction for the identified data sources, likely 31/12/2014.

Follow-up: Data from randomized placebo-controlled trials have shown that bisphosphonates are effective to reduce fracture risk only after at least 6 months of continuous use (27). That is not the case though for adverse events, which can be observed immediately after bisphosphonate therapy initiation (14, 17, 28). Therefore, different follow-up windows will be established, as follows:

- Safety outcomes (WP1 and WP3): Patients will be followed from the latest of the following dates
- a) Start of study period
- b) One year of valid data in database
- c) Date of incident prescription of bisphosphonate (after one year of non-use)

until the earliest date of:

- a) The end of enrolment in the database (due to moving out or death)
- b) Date of last data update in the database
- c) Stopping of treatment +30 days (no repeat prescription within 1 month)
- d) Switch of treatment to other (non-bisphosphonate) osteoporosis medication

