- e) Outcome of interest (different date for each study outcome)
- Effectiveness outcomes (WP2 and WP4): Patients will be followed from the latest of the following dates
- a) Start of study period
- b) One year of valid data in database
- c) Date of continued prescriptions of an oral bisphosphonate for 6 months after the date of therapy initiation

until the earliest date of:

- a) The end of enrolment in the database (due to moving out or death)
- b) Date of last data update in the database
- c) Stopping of treatment +180 days (no repeat prescription within 6 months)
- d) Switch of treatment to other osteoporosis medication, with no repeat prescription of oral bisphosphonates within the next 6 months
- e) Incident recorded fracture (WP2) or last BMD measurement available (WP4)

SAMPLING

One of the advantages of routinely collected datasets is that the contained information is readily available, not needing active recruitment. Therefore, all patients eligible (see target population and exclusion criteria above) registered in the chosen data sources will be included.

Sample size/power: According to feasibility counts provided by CPRD, the number of eligible patients (with an eGFR<45 and possible to link to HES) would be of 204,528 subjects, and 34,127 (16.7%) of these received oral bisphosphonate prescriptions. These numbers would provide statistical power to reliably answer each of the study aims, as it can be seen below:

Work-package 1: In a survival analysis (log-rank 2-sided test), accepting 5% type I error and 20% attrition from propensity score matching and loss to follow-up in 2 years, and assuming CKD stage progression rates of 12/100 person-years (29), the available number of participants would provide 90% power to detect an excess risk of CKD progression of 10% or more (HR \geq 1.10) associated with oral bisphosphonate use.

Work-package 2: In a log-rank (2-sided) test, and accepting 5% type I error and 20% drop-out, with 2 years of follow-up and an expected fracture rate of 103/10,000 person-years in CPRD data (30), the available sample size would provide 90% power to detect a fracture reduction of at least 15% (HR≤0.85) amongst oral bisphosphonate users (compared to non-users).

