Sensitivity analyses: Three pre-defined interactions will be tested for, and if significant, stratified analyses will be reported: 1.by gender; 2.by history of previous fracture; and 3.by CKD stage.

In addition, a sensitivity analysis will be carried out to test whether the observed association/s between bisphosphonate use and each of the outcomes follows a gradient, one of the Bradford-Hill criteria of causality (46). To do this, bisphosphonate users will be categorized according to their medication possession ratio (MPR). MPR is calculated as the number of defined daily doses prescribed over the total number of days of follow-up, and it is therefore an approximation of adherence in CPRD and similar datasets.

Bisphosphonate users will then be grouped into: low adherence (MPR <0.4), intermediate adherence (MPR 0.4 to <0.8) and high adherence (MPR \ge 0.8), and HRs will be estimated for each of these categories when compared with matched bisphosphonate non-users.

A post-hoc analysis has been proposed to study the association between bisphosphonate use and hypocalcaemia/hypophosphataemia: given the low number of study participants with the proposed outcome of interest (hospital admission for calcium/phosphate alterations), data has been extracted on laboratory values of serum calcium and phosphate as available in primary care records (CPRD). Hypocalcaemia/hypophosphataemia as defined by these values will be analysed as a secondary outcome for WP3 in addition to the proposed main outcome.

DISSEMINATION AND PROJECTED OUTPUTS

OUTPUTS

A detailed report of our study, including all the work undertaken, will be published in the NIHR HTA Journal. A number of research papers will also be published to report key findings in national and international scientific journals including the Lancet, the British Medical Journal, the Journal of Bone and Mineral Research, Osteoporosis International, Journal of the American Society of Nephrology, or Kidney International, amongst others. Where available, we will publish our findings in open access, and we have requested funding to cover related fees, which range from £1,800 (Osteoporosis International) to £3,000 (BMJ).

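### Adherence bands are computed over a follow-up that the outcome itself ends, so a drug with no effect would show more events with better adherence

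*Protocol*

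**What the plan says.** **Sensitivity analyses.** The protocol will test whether each association "follows a gradient, one of the Bradford-Hill criteria of causality". It does this with the medication possession ratio (MPR): "MPR is calculated as the number of defined daily doses prescribed over the total number of days of follow-up". Users are grouped as "low adherence (MPR <0.4), intermediate adherence (MPR 0.4 to <0.8") or high (0.8 and above), and "HRs will be estimated for each of these categories when compared with matched bisphosphonate non-users".

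**Follow-up, safety outcomes (WP1 and WP3).** The clock starts at the latest of several dates, among them "Date of incident prescription of bisphosphonate (after one year of non-use"). It ends at the earliest of several dates, among them "Stopping of treatment +30 days (no repeat prescription within 1 month") and "Outcome of interest (different date for each study outcome").

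**Follow-up, effectiveness outcomes.** For WP2 the clock starts only after six months of continued prescribing. It ends, among other reasons, 180 days after stopping or at the fracture.

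**Exposure periods.** Two prescriptions are joined when the gap between the end of one and "the start of the second of the two prescriptions was less than 30 days apart".

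**Immortal time bias and time-varying exposure.** The only time-varying element described is that time before the first prescription counts as non-use. Nothing in the protocol updates MPR over time, lags it, or fixes it in a window before the risk time.

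**The concern.** A baseline-style group in a Cox model must be known before the time at risk that it is meant to explain. Here the denominator of the grouping variable stops at the event. An event during a supply shortens the denominator while the doses already issued stay in the numerator, which raises MPR. A user who stops without an event has up to 30 unmedicated days added (180 in WP2), which lowers it.

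The protocol puts this analysis forward as evidence on causality. A false rise of events with adherence would look like dose-related harm for CKD progression and adverse events. It would also hide or reverse a real protective gradient for fracture. Those are the two sides of the study's question, and the results are meant for NICE and the MHRA.

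**Working it through.** **1. Inputs.** The protocol gives no result for this analysis beyond the band limits, so there is no figure to reproduce.

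- From the protocol (Sample size/power): 12 events per 100 person-years for WP1; 103 per 10,000 person-years for WP2; a 2% two-year incidence for WP3.
- Assumed, because the protocol gives no values: supplies of 28, 56 or 84 days (14 also tried) at one defined daily dose (DDD) per day; 3–10% stopping per 28 days; 0–80% of refills late by 1–29 days (WP2: 30% late, by up to 29, 60 or 120 days); a cap of 2 or 5 years.

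**2. Mechanism by hand (WP1/WP3).**

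- One 28-day supply, event on day 10: 28/10 = 2.8, high band.
- The same supply, stopped without an event: 28/(28+30) = 0.48, intermediate band.

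The prescribing is identical and the outcome decides the band. For an event-free user with S days of supply and no gaps, MPR = S/(S+30). This is below 0.8 only if 0.2S < 24, so S < 120 days. Five 28-day supplies give 140/170 = 0.82, still high.

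**3. Null simulation, WP1** (true hazard ratio 1; 5% stopping per 28 days; 30% of refills late; 2-year cap; 300,000 users). The ratio is the band's event rate over the true common rate.

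| Supply | Low, % users | Intermediate, % users / ratio | High, % users / ratio | Control: intermediate / high ratio |
|---|---|---|---|---|
| 28 days | 0.0 | 38.0 / 0.40 | 62.0 / 1.17 | 0.99 / 1.00 |
| 56 days | 0.0 | 23.0 / 0.15 | 77.0 / 1.07 | 0.99 / 0.99 |
| 84 days | 0.0 | 16.2 / 0.08 | 83.8 / 1.04 | 1.00 / 1.00 |

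The control bands users on treatment history up to the censoring date, ignoring the event. With 28-day supplies, banding as written puts 3,622 of 41,382 events (8.8%) in the intermediate band. The control puts 9,288 of 41,254 (22.5%) there.

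Across all WP1/WP3 runs with 28- to 84-day supplies, the intermediate ratio was about 0.05–0.82 and the high ratio about 1.0 to well above 2. Late refills matter most. With 28-day supplies, 8% stopping per supply and a 5-year cap, moving the late share from 0 to 100% took the intermediate ratio from 0.13 to 0.79. The high ratio went from 1.08 to about 40, by which point only about 3% of users were left in that band.

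**4. In the planned model.** A Cox model stratified by matched set (1:5, 4,000 sets, 28-day scenario of step 3) gave hazard ratios of 0.36 (95% CI 0.27–0.50) intermediate and 1.22 (1.11–1.35) high. The overall user hazard ratio was 1.04 (0.95–1.14).

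**5. WP2-type rules** (180-day tail; 30% of refills late). Examples:

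| Supply, stopping per 28 days, longest delay | Low | Intermediate | High |
|---|---|---|---|
| 28 days, 5%, 29 days | 0.33 | 0.43 | 1.67 |
| 28 days, 5%, 120 days | 0.50 | 0.80 | 6.74 |
| 84 days, 5%, 120 days | 0.16 | 0.55 | 1.58 |

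Controls ran from 0.96 to 1.05. A separate run gave 0.52, 0.83 and 7.4. Overall: 0.16–0.52 low, 0.30–0.83 intermediate, 1.6–7.4 high.

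**6. Can the low band be reached?** In WP1/WP3 the lowest MPR at one DDD per day is d/(d+30) for a supply of d days: 28/58 = 0.48, 56/86 = 0.65, 84/114 = 0.74. Adding late refills barely moves it: n supplies of 28 days give 28n/(28n + 29(n−1) + 30) = 28n/(57n+1), which rises from 0.483 to 0.491. MPR below 0.4 needs 0.6d < 12, so d < 20 days.

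The exceptions are short supplies (14/44 = 0.32; 3–7% of users in the low band in simulation) and doses below one DDD per day (at 0.5, 14/58 = 0.24). In WP2, S/(S+180) < 0.4 holds for any S < 120, and 14–40% of users fell in the low band.

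**The case against.** Five points can be made for the plan.

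- **It is only a sensitivity analysis.** True. The main user-versus-non-user hazard ratios do not use MPR, and WP4 uses linear regression. A reader might infer that the main results are compromised; the documents do not support that.
- **The size is unknown.** This also stands. The protocol states no supply lengths, stopping rates or refill delays, so no single ratio can be quoted. In the mildest runs the high band sat at about 1.00 and the distortion showed only as a depressed intermediate band. The direction did not change in any run.
- **Counting doses only up to the event would cure it.** It does not. With 28-day supplies the ratios were still 0.65 and 1.11.
- **The low band is not simply empty.** Correct. A reader might infer from the 30-day rules that nobody can fall below 0.4. That holds only in WP1/WP3, for supplies of 20 days or more at one DDD per day. The protocol gives no DDD values, and Appendix 1 lists several strengths of the same drug. At 0.5 DDD per day with every refill late, about 97% of users fell below 0.4.
- **Not every event-free stopper is downgraded.** Also correct. Without gaps this needs under 120 days of supply. In WP2 the day-10 example does not carry over directly, because entry comes after six months of prescribing. There the argument rests on the WP2-type simulations.

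One might answer that a statistical analysis plan could settle this. But the protocol states the denominator and the end of follow-up explicitly, so this is a rule that has been fixed, not a detail left open.

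**Conclusion.** The definition is wrong as written. Dividing by total follow-up, when follow-up ends at the outcome, makes the adherence band depend on the event. Under no drug effect it produces a false gradient of more events with better adherence, of the sizes in steps 3 to 5 above. Those sizes rest on the assumed refill behaviour and on a constant hazard unrelated to adherence.

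The planned gradient cannot be read as evidence on causality: it would mimic harm in WP1/WP3 and mask or reverse benefit in WP2. As a secondary and conditional point, the 0.4 cut-off leaves the low band unreachable in WP1/WP3 for supplies of 20 days or more unless the prescribed dose is below one DDD per day. The planned three-level comparison may then have only two levels. The change should be made, although the primary analyses do not depend on it.

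**What to change.** Replace whole-follow-up MPR with exposure known before the risk time, in one of two ways.

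- **Time-updated:** MPR to date, cumulative DDDs, or duration of use, entered as a time-varying term in the Cox model. On the null WP1 data of step 3 (28-day supplies), time-updated MPR gave 0.99 intermediate and 1.00 high.
- **Fixed window:** MPR over an initial period, with outcome follow-up starting after the window in both users and matched non-users. A six-month window gave 1.01 and 1.00.

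Set the cut-offs from the MPR distribution that the follow-up rules allow, without looking at outcomes. The low band stayed empty in these WP1 runs even after the correction. Keeping early stoppers in order to fill it is not a free remedy: it would conflict with the censoring 30 days after stopping in WP1/WP3 and with the six-month entry rule in WP2.

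The cost is a change of wording and modest programming. The fixed-window version also loses events and users who leave follow-up within the window. In the simulated six-month case 14,118 + 61,089 = 75,207 of 100,000 users remained, a loss of about 25% under the assumed 5% stopping per 28 days. The time-updated version avoids that loss.

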Propensity Score matching: Propensity scores represent the probability that a patient will receive the drug of interest (i.e. oral bisphosphonates) according to their baseline sociodemographics and clinical characteristics. Multivariable logistic regression equations will be used to calculate one propensity score for each of the study outcomes of interest (36). Prespecified predictors of each of these outcomes will be included in each of these equations (37). Finally, the created propensity scores will be used to match bisphosphonate users to comparable non-users with a caliper matching technique with a maximum caliper width of 0.02 standard deviations (SDs). In short, this means that bisphosphonate non-users will only eligible to be matched if their propensity score falls within a bandwidth of 0.02 SDs of the bisphosphonate user subject's propensity score. This method has been shown to be the most efficient to minimize confounding by indication in pharmacoepidemiological studies (6) and typically excludes the small proportion of patients with extremely high or extremely low risk

for the outcome that are not present in both intervention and comparator patient samples. Covariate balance achieved through PS matching will be assessed using absolute standardized difference in means or proportions.

Some confounders, such as smoking, alcohol drinking, body mass index might not be completed. We will impute them for the propensity score (logistic) models using multiple imputation by chained equations (MICE) methods. 10 imputed datasets will be used. For each imputed dataset, a ps matched dataset will be identified and analysed as per study outcome separately. Outcome estimates of 10 ps imputed datasets will be then combined using Rubin's rules to obtain an overall outcome estimate (46).

Absolute rates of study outcomes: The crude and age and sex specific incidence rates (and 95% confidence intervals) of each of the events will be estimated separately in the cohort of oral bisphosphonate users and amongst propensity score-matched non-users assuming a Poisson distribution. Kaplan-Meier plots will be created to show the predicted cumulative probability of each of the study endpoints according to bisphosphonate use.

In addition, annualized eGFR (secondary outcome in WP1) and BMD (WP4) changes and 95% confidence intervals will be reported.

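### Propensity matching on any bisphosphonate use does not balance each adherence band against its matched non-users, so the medication possession ratio analysis can show a gradient for a drug with no effect

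*Protocol*

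**What the plan says.** Under Data Analysis, Propensity Score matching, the score is the "probability that a patient will receive the drug of interest (i.e. oral bisphosphonates) according to their baseline" characteristics, with one score per outcome built from pre-specified outcome predictors. The Study Design section describes 1:5 matching as "producing matched comparable (in terms of observed baseline characteristics) cohorts". The check is stated once: "Covariate balance achieved through PS matching will be assessed using absolute standardized difference in means or proportions". Under Hazard ratios, the Cox model is stratified by matched set.

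Under Sensitivity analyses, users alone are then split: "MPR is calculated as the number of defined daily doses prescribed over the total number of days of follow-up", with bands "low adherence (MPR <0.4), intermediate adherence (MPR 0.4 to <0.8) and high adherence" (0.8 or more). For the comparison, "HRs will be estimated for each of these categories when compared with matched bisphosphonate non-users". The stated purpose is to see whether the association "follows a gradient, one of the Bradford-Hill criteria of causality". The section names no balance check, re-matching or covariate adjustment by band.

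**The concern.** The comparability that matching provides is between all users and all matched non-users. MPR is observed only in users and only after treatment starts. A baseline trait that affects both adherence and outcome risk can be balanced overall and still be under-represented in one band and over-represented in another. The matched non-users of a band resemble its users on the score for any use. They need not resemble them on the traits that sort users into that band.

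This matters because the protocol fixes the banding, the comparator and the causal reading of the result in the same place. A graded set of hazard ratios produced by who adheres, not by the drug, would be counted towards causality. If lower-risk patients adhere better, this mechanism alone would suggest fracture benefit in WP2, and in WP1 and WP3 it would tend to hide harm.

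**Working it through.** The protocol gives no figure for this analysis, so there is none to reproduce. The size below rests on stated assumptions.

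**1. Closed-form illustration.** Assumed, not in the documents: the drug has no effect; a baseline condition is present in 30% of users and of matched non-users and multiplies the hazard by 2; high adherence occurs in 30% of users with the condition and 60% of users without it; all other users form one group.

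- Prevalence in the high band: 0.3×0.3 / (0.3×0.3 + 0.7×0.6) = 0.09/0.51 = 0.176.
- Prevalence in the rest: 0.3×0.7 / (0.3×0.7 + 0.7×0.4) = 0.21/0.49 = 0.429.
- HR against non-users = (1 + band prevalence) / (1 + 0.30): high band 1.176/1.30 = 0.905; rest 1.429/1.30 = 1.099.

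With a weaker link (condition HR 1.5, 10-point gap, so 50% against 60%):

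- The prevalences are 0.15/0.57 = 0.263 and 0.15/0.43 = 0.349.
- The HRs are (1 + 0.5×0.263)/1.15 = 0.984 and (1 + 0.5×0.349)/1.15 = 1.021.

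**2. Does the planned matching and stratification prevent it?** A null drug was simulated on the assumptions of step 1, with 1:5 matching, the 0.02 SD caliper, the condition in the score and Cox regression stratified by matched set.

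- Prevalence after matching was 36.8% in users and 36.9% in non-users.
- The standardized difference was −0.30 in the high band and +0.26 in the rest.
- The HRs were 0.92 and 1.08. Adding the score's own covariates to the same model gave 1.00 and 1.00.
- A separate simulation gave 0.92 and 1.11, returning to 1.00 and 1.02 after adjustment.

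**3. How much does set stratification remove?** This uses three bands (assumed shares 25/25/50%) and a continuous risk factor with HR 1.5 per SD and correlation −0.3 with adherence. HRs for a null drug:

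| What drives the score | Low | Intermediate | High |
|---|---|---|---|
| The factor alone | 1.00 | 1.00 | 1.00 |
| The factor and another covariate equally | 1.08 | 1.02 | 0.95 |
| Mostly other covariates | 1.15 | 1.03 | 0.91 |

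In the last row the standardized difference is 0.00 overall but +0.36, +0.09 and −0.23 by band. With the factor outside the score and unrelated to adherence, the HRs are 1.00, 0.99 and 1.01.

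**4. The MPR definition pulls the other way.** The denominator is days of follow-up, and under Follow-up in Setting/Context the outcome ends follow-up. A null drug with no health factor was simulated under those rules. Assumed: 28-day prescriptions, coverage of 0.5–1.0 while treated, 0.5 stops per year, at most 5 years. HRs from low to high band were 0.27, 0.69 and 2.91 with the 180-day tail. With the 30-day tail at 12/100 person-years they were 0.05, 0.75 and 1.41. An early event shortens the denominator and raises MPR.

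**5. Would the false signal be detected?** This takes 34,127 users from the Sampling section, less 20%, so 27,302; the Summary gives 4,127, which would lower every figure here. Two-year risk is 1 − exp(−0.24) = 21.3% for WP1 and 1 − exp(−0.0206) = 2.04% for WP2, giving E = 5,825 and 557 events among users. For the high band, with share s of users, z = |ln HR| / √(1/(E·s·HR) + 1/(5·E·s)), and power is Φ(z − 1.96) + Φ(−z − 1.96).

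| Condition HR, gap | s | HR | WP1 z, power | WP2 z, power |
|---|---|---|---|---|
| 1.5, 10 points | 0.57 | 0.984 | 0.84, 13% | 0.26, 6% |
| 1.5, 20 points | 0.54 | 0.966 | 1.74, 41% | 0.54, 8% |
| 2.0, 30 points | 0.51 | 0.905 | 4.76, >99% | 1.47, 31% |

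These figures concern the adherence mechanism alone, without step 4.

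**The case against.** **Premise.** The protocol contains no data showing that healthier patients adhere better. A reader might infer that they will collect in the high band and that a null drug will show a protective gradient. The documents do not support that. Without the link this mechanism produces nothing, and step 4 shows a larger distortion in the opposite direction under the rules as written. This objection stands: the bias can occur, and its net direction is unsettled.

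**Stratification.** Retaining matched sets removes the part of the imbalance carried by the score, and outcome predictors are in each score. This stands in part. Protection is complete only when the adherence-related trait alone drives the score (step 3).

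**Size.** It is tempting to set the between-band ratio 0.905/1.099 = 0.82 beside the 0.85 for which WP2 is sized. The plan estimates each band against non-users, so the like-for-like figure is 0.90. Nor can WP1's high detection probability be carried over to fractures, where it is 6% to 31% in these scenarios.

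**Scope.** Band-level balance tables may be left to a statistical analysis plan that is not shown, this is a sensitivity analysis, and no decision rule is attached. That limits the weight of the point. But the protocol itself fixes the comparison and its causal interpretation. The Rosenbaum bounds in Methods address unobserved confounders and are not tied to the bands, whereas here even measured covariates can lose balance.

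**Conclusion.** The structural point holds. Balance on the propensity for any use does not ensure balance between an MPR band and its matched non-users, even for covariates in the score, and the plan names no step that would detect or correct this. If measured baseline risk is related to adherence, a null drug can give a high-band HR of about 0.90 with about 1.10 in the rest (30% prevalence, condition HR 2, 30-point gap). At the weaker link in step 1 the HRs are 0.98 and 1.02. All these inputs are assumptions; the true size cannot be computed from the protocol.

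The consequence is confined to the gradient analysis. As planned it is open to two biases of opposing direction and unknown net effect, so neither the presence nor the absence of a gradient can be read as evidence on causality. The main hazard ratios for WP1 to WP3 are unaffected. A modest change is worth making.

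**What to change.** In the MPR paragraph under Sensitivity analyses:

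1. Report the absolute standardized differences within each band, comparing its users with their own matched non-users.
2. Add the pre-specified propensity-score predictors as covariates to the set-stratified band models.
3. Do not read a gradient as support for causality on this adjustment alone. Also measure MPR so that it does not depend on the outcome date, for example in a fixed window with follow-up starting after it, or as time-varying cumulative exposure. State residual confounding by unmeasured adherence-related behaviour as a limitation.

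Items 1 and 2 use data already held and cost one table, one extra model per outcome and slightly wider intervals. Item 3 needs some further programming, and a fixed window gives up the events that fall inside it. Item 2 corrects only for measured traits and leaves the event-truncated MPR untouched, so the three belong together.
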